### Barriers to Quitting Smoking Among Those with HIV/AIDS

While there are limited data on specific barriers to quitting smoking that are unique to individuals with HIV/AIDS compared to the general population, two factors may be important. First, smoking cessation interventions for individuals with HIV/AIDS may need to address psychiatric history/comorbidity, most commonly depression and dysthymia (Nahvi & Cooperman, 2009). A large epidemiological study using a nationally representative sample found that more than a third of HIV+ patients exhibited major depression and another quarter had dysthymia (Bing et al., 2001). A meta-analysis of studies has shown that the risk for depression is 2-times greater if one is diagnosed with HIV/AIDS, compared to unaffected individuals (Ciesla & Roberts, 2001) which may be an under-estimate of risk (Asch et al., 2003). Symptoms of psychological distress, including depression symptoms, have been shown to be a strong risk factor for relapse following successful smoking cessation in the general population (Zvolensky et al., 2009) and have been associated with lower levels of motivation to quit smoking (Burkhalter et al., 2005) and higher risk of smoking (Webb et al., 2007) among those with HIV/AIDS. Second, smoking cessation interventions for individuals with HIV/AIDS may need to address cognitive impairment, which typically includes difficulties with memory, attention/concentration, and executive function (Heaton et al., 2011). While the advent of HAART has reduced the rate of cognitive impairment among those with HIV/AIDS, several recent surveys indicate that 39%-69% of individuals with HIV/AIDS show cognitive impairment (Robertson et al., 2007; Simioni et al., 2010). In the general population, smokers use nicotine to enhance cognitive function, nicotine withdrawal increases cognitive impairment which predicts relapse, and resuming smoking ameliorates abstinence-induced cognitive impairment (Heishman, 1999; Evans & Drobis, 2009; Rukstalis et al., 2005). Consequently, nicotine dependence treatments for individuals with HIV/AIDS may show greater efficacy if they adequately address the patient's relatively high level of psychological distress and cognitive impairment.

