#### Mediating Variables.

##### Mood: Positive and Negative Affect

The Positive and Negative Affect Schedule (PANAS; Watson et al., 1988), a 20-item self-report measure, assesses positive (PA; 10 items, e.g., enthusiastic) and negative (NA; 10 items, e.g., distressed) affect. The inclusion of PA is a strength since it is less frequently examined as a mediator of smoking cessation. The PANAS subscales are internally consistent ( $\alpha = .84\text{--}.91$ ) and exhibit good validity (Watson et al., 1988). The depression and anxiety scales described above will be mediators as well. The PANAS will be administered at Pre-Quit, Target Quit Day, and Weeks 3, 7, and 12.

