of 20 trials. During the 0-back, participants are instructed to press the SPACEBAR if the stimulus appears in a predetermined location (designated as the upper left corner of the computer screen). The 0-back serves as a baseline condition of the n-back, during which participants are engaged in a task that does not require storage or manipulation of information in working memory, but is otherwise analogous to the other n-back conditions. During the 1-back, participants are instructed to press the SPACEBAR whenever the stimulus appears in the same location as the stimulus that immediately preceded it and to do nothing if the stimulus appears in any other location. During the 2- and 3-back conditions, participants are instructed to press the SPACEBAR whenever the stimulus appears in the same location as the stimulus that preceded it by 2 or 3 trials, respectively. The primary dependent variables for this task are total number of correct responses and reaction time. Time: approximately 16 min.

- Penn Continuous Performance Test - Number/Letter Version (PCPT-nl). The PCPT-nl is a measure of visual attention and vigilance based on the Penn CPT (Kurtz et al., 2001). In this task, a series of red vertical and horizontal lines (7-segment displays) flash in a digital numeric frame (resembling a digital clock). The participant must press the spacebar whenever these lines form complete numbers or complete letters. The task is divided in two parts, each lasting three minutes: in the first part the participant is requested to respond to numbers and in the second part the response is to letters. The participant practices both sets of trials before the task begins. Time: approximately 10 min with practice.

For both measures, median reaction time for correct responses measures cognitive performance. These tasks will be administered at Pre-Quit, Target Quit Day, and Weeks 3 and 12.

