Aim 2: The analyses are a comparison in week 12 and 24 differences in QOL and severe side effects. For QOL, the overall scale mean among HIV/AIDS patients is 58.3 (SD = 24.5, Range 14-100; Holmes & Shea, 1998). We have 80% power to detect a mean difference of 7.8 at any time-point between the treatment arms with the proposed sample of 310. For side effects, the analyses will involve a test of non-inferiority since we cannot use standard statistical tests and conclude that a non-significant comparison shows that the drug is safe (i.e., "the absence of evidence is not evidence of absence"). In our past study with varenicline, 61% of participants on varenicline reported no severe side effects, vs. 76% of participants on placebo, a 15% difference (Patterson et al., 2009). With the present sample size, we will have 80% power to detect similar equivalence between treatment arms in terms of the frequency of severe side effects over the course of the 12-week treatment, given that side effects are actually non-significantly different across the treatment arms.

Aim 3: The analyses will assess changes in affect and cognitive function as mediators of treatment arm effects at week 12 and 24. These measures are continuous difference scores. Our sample of 310 is well above the minimum sample of 200 recommended for models of this size (Haduk, 1987; Boosma & Gabrielli, 1985). The mediation hypothesis will examine the proportion of treatment effect explained (Lin et al., 1997; Vittinghoff et al., 2009), and will test each mediation hypothesis with a z-score generated using the delta method. Our sample of 310 gives us 80% power to observe small effects in a 1-sample test ( $\delta=0.20$ ) when testing at  $\alpha=0.05$ . There are four proposed mediating pathways (2 measures of affect and cognition, respectively) between treatment and outcome, so our type-1 error will be corrected to 0.0125. Our sample of 310 gives us 80% power to detect small to medium effects ( $\delta=0.19$ ) for changes in the proposed mediators, which we have seen in previous trials (Patterson et al., 2009; [name] et al., 2010a).

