**Aim 2: Assess effects of varenicline therapy on QOL and side effects.** Repeated-measures MANOVA will examine differences across treatment arms in QOL (total scale score and subscale scores) over the trial. Participant covariates will be included, such as medical treatment history. In addition, we will compare treatment arms in terms of the frequency of severe side effects (*individual, including cardiovascular side effects, and total*). Using logistic regression, we will test against the lower boundary on percent reporting only mild-moderate (i.e., < severe) side effects. The hypothesis test for equivalence is a test of whether the OR is out of the prescribed range for the difference between the treatment arms. This approach provides a more valid test of the potential safety of varenicline for individuals with HIV/AIDS vs. a simple comparison of mean responses on a side effects measure. *We will also examine if participants on tenofovir (vs. other HAART) experience a greater frequency or more severe varenicline side effects by including type of HAART as a covariate in these analyses and, if so, we can explore if this relationship is mediated by varenicline plasma levels using a regression-based path model. Lastly, we will also examine if the frequency of cardiovascular side effects is different between treatment arms while considering if participants are currently taking HAART or not by including a covariate for current HAART use in the logistic regression models of side effects.*

**Aim 3: Assess changes in affect and cognitive impairment as mediators of varenicline therapy's effect on quit rates.** We will use a regression-based path model approach to examine mediation of treatment effects based on MacKinnon et al. (2007). All variables will be standardized for the analyses. Candidate mediators include positive and negative affect and two cognitive performance task measures. Suspected mediators will be entered as standardized pre-post differences, continuously distributed and treated as normal in linear regression. The effects of treatment arm on mediators, and of mediators on outcome, will be assessed using linear regression and standardized variables. We will focus on changes in

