mediators from baseline to week 3, since abstinence-induced withdrawal effects typically peak within the first 3 weeks of cessation (Hughes, 2007) but we can examine delayed changes to weeks 5, 7, and 9 as well. We will then assemble the path model using “seemingly unrelated estimation” methods (Beasley, 2008; Zellner, 1962). The path model partitions the effect of treatment on outcome into direct (and unexplained) effects vs. mediated effects. We will then test the overall mediation hypothesis using the proportion of treatment effect explained (Lin et al., 1997; Vittinghoff & McCulloch, 2009), and the strength of each mediating pathway as follows. We will estimate the model for standardized treatment predicting abstinence without mediators to estimate the direct effect of treatment in the unadjusted model ( $\beta^*$ ). We will then test whether treatment predicts each of the suspected mediators and, in turn, test whether mediators predict abstinence in an adjusted treatment model and estimate the effect of treatment in the mediator adjusted model  $\hat{\beta}^*$ . Finally, we will calculate the proportion of treatment effect explained, which is calculated as  $(\hat{\beta}^*/\beta^*)$ ; the standard error for this quantity is calculated using the delta method, and the mediation hypothesis will be tested using a z-test. Individual pathways will be tested using products of the coefficients along each path using a delta-method based z-test.

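### Aim 3 does not adjust the mediator change scores for their Week 0 values, so the mediator-to-abstinence path is biased if baseline level also affects quitting

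*Combined protocol and SAP*

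**What the plan says.** The Aim 3 text under Data Analysis names four mediators: "Candidate mediators include positive and negative affect and two cognitive performance task measures". On their form it says: "Suspected mediators will be entered as standardized pre-post differences, continuously distributed and treated as normal in linear regression". The Power section agrees: "These measures are continuous difference scores". Standardization is general: "All variables will be standardized for the analyses". The main window is the change in "mediators from baseline to week 3, since abstinence-induced withdrawal effects typically peak within the first 3 weeks of cessation".

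The models are then listed: arm predicting each mediator, and mediators predicting abstinence with arm in the model. Individual pathways are tested by products of coefficients with a delta-method z-test, and overall mediation by the proportion of treatment effect explained. No Week 0 mediator value appears in either equation.

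That value is collected. For affect: "The PANAS will be administered at Pre-Quit, Target Quit Day, and Weeks 3, 7, and 12". For the cognitive tasks: "These tasks will be administered at Pre-Quit, Target Quit Day, and Weeks 3 and 12".

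Three other provisions could bring a baseline value in, but none ensures it:
- The general covariate rule in Data Analysis selects on association with arm or with follow-up completion.
- The missing-data rule selects on association with missingness at p < .05.
- The Depression and Anxiety section allows HADS as a covariate, but only as an option and only for HADS.

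**The concern.** Participants with high distress at Week 0 tend to fall most by Week 3 through regression to the mean alone, so the change score carries information about the starting level. Dividing the difference by its SD does not remove this. Arm is randomized, but the amount of change is not. If starting level has its own effect on quitting, it therefore confounds the change-to-abstinence coefficient.

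The plan's own Background makes this plausible for mood: it says that symptoms of psychological distress "have been shown to be a strong risk factor for relapse following successful smoking cessation".

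Aim 3 has a directional hypothesis and its own corrected alpha of 0.0125. Both of its test quantities use the exposed coefficient, so a real mediator could be missed or a path reported that reflects only baseline differences.

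**Working it through.** **The plan's own figure.** Power for Aim 3 is stated as 80% at N = 310, δ = 0.19 and two-sided alpha 0.05/4 = 0.0125. One-sample z-test: 0.19 × √310 = 3.345; 3.345 − 2.498 = 0.848; Φ(0.848) = 80.2%. It reproduces. It does not concern the form of the mediator model, and the fix changes no stated N, alpha or power figure.

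**Algebra.** Let M0 and M3 be the Week 0 and Week 3 scores with equal variances and correlation r within arm, and D = M3 − M0.
- corr(D, M0) = −√((1 − r)/2): −0.59 at r = 0.3, −0.50 at 0.5, −0.39 at 0.7, −0.32 at 0.8.
- cov(D, M0)/var(D) = −(1 − r)/(2(1 − r)) = −1/2. If abstinence depends on g·D + h·M0, the coefficient on D with M0 left out is g − h/2.
- If only the Week 3 level matters, with effect b, then b·M3 = b·D + b·M0. So g = h = b and the unadjusted coefficient is b/2, whatever r is.
- With D in SD units, as planned, the coefficient is g − h·√((1 − r)/2).

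**Check by simulation.** N = 310, logistic outcome, one mediator scored so that higher is worse, arm effect −0.3 on the Week 3 score, 600 runs per setting. g is the log-odds per SD of change and h per SD of Week 0 level. These inputs are assumptions, because the documents give no r and no h.

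| r | g | h | Formula | Without M0 | With M0 |
|---|---|---|---|---|---|
| 0.5 | 0 | −0.4 | +0.20 | +0.203 | +0.002 |
| 0.7 | 0 | −0.4 | +0.155 | +0.152 | −0.004 |
| 0.5 | −0.3 | −0.4 | −0.10 | −0.089 | −0.300 |
| 0.7 | −0.3 | −0.4 | −0.145 | −0.147 | −0.311 |
| 0.5 | −0.3 | +0.2 | −0.40 | −0.403 | −0.305 |
| 0.7 | −0.3 | +0.2 | −0.377 | −0.379 | −0.301 |
| 0.5 | −0.3 | 0 | −0.30 | −0.319 | −0.320 |
| 0.7 | −0.3 | 0 | −0.30 | −0.298 | −0.300 |

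The rows show, in pairs, a created path, a weakened path, an inflated path and no distortion.

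**How often a false coefficient appears** (155 per arm, alpha 0.0125, only Week 0 level affects abstinence):
- Log-odds 0.5 per SD: about 43% at r = 0.3, 26% at 0.5 and 8% at 0.8, against about 1–2% with M0 in the model.
- Log-odds 0.4: 17%, 9% and 6% at r = 0.5, 0.7 and 0.8.
- Log-odds 0.2: 5%, 4% and 3%.

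These rates are for the mediator-to-abstinence coefficient. The product test also needs the arm-to-mediator path and rejects less often. In the table's g = 0, h = −0.4 rows it rejected in 10% (r = 0.5) and 9% (r = 0.7) of runs at alpha 0.05, against 1% adjusted. At 0.0125 it rejected in 1% or fewer either way.

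**Arm-to-mediator path.** Randomization keeps this unbiased; only precision changes. With M in SD units, residual variance is 2(1 − r) for change and 1 − r² after adjustment, a ratio of (1 + r)/2 = 0.75 at r = 0.5. For an assumed arm effect of 0.35 SD with 155 per arm:
- Unadjusted: SE = √(2 × 1.00/155) = 0.1136; 0.35/0.1136 − 2.498 = 0.58; power 72%.
- Adjusted: SE = √(2 × 0.75/155) = 0.0984; 0.35/0.0984 − 2.498 = 1.06; power about 85–86%.

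Simulation gives about 71% against 84–86%.

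**The case against.** The strongest reply is that the plan's hypothesis is about change. Aim 3 is worded in terms of changes in affect and cognition, and the Week 3 window is justified by withdrawal effects that arise on quitting. If only the change drives abstinence, h = 0 and the planned model is unbiased. It is then also more powerful, because adding the baseline inflates the variance of the change coefficient by 2/(1 + r), or 1.33 at r = 0.5. Mediator-path power at r = 0.5 is then about 92% unadjusted against 81% adjusted at log-odds 0.5 per SD, and 73% against 58% at 0.4. All of this stands. But the plan neither states nor defends the assumption that h = 0.

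The evidence for a level effect is also uneven. The Background sentence concerns distress and depression symptoms, not Week 0 PANAS scores, and it does not mention positive affect. For cognition, the Background describes impairment brought on by withdrawal, which is a change. For the two task measures, baseline confounding is possible rather than documented.

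A reader might infer that omitting the baseline would falsely confirm the Aim 3 hypothesis. The direction argues against that. If high Week 0 distress lowers quitting, the spurious coefficient is positive: larger falls in distress appear to predict less abstinence. With a drug that lowers distress, the resulting indirect effect opposes the hypothesis.

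**Conclusion.** The gap is real, and its effect is conditional. The plan leaves the Week 0 value out of both Aim 3 equations and nothing else in the documents ensures it. The mediator-to-abstinence coefficient is then biased by −h/2 on the linear scale whenever Week 0 level matters given the change, and the bias carries into the product of coefficients and the proportion explained. Size and direction are unknown, because the documents give neither r nor h; every rate above rests on assumed values and equal variances.

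A reader might conclude that Aim 3 must give a wrong answer. The documents do not support that: with h = 0 there is no bias, and with a small h the distortion is modest. Nor is the arm-to-mediator path biased; there, adjustment only gains precision. The point should be fixed as a cheap improvement to a mechanism aim. The quit-rate comparison in Aim 1 and the quality-of-life and side-effect analyses in Aim 2 are untouched.

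**What to change.** In the Aim 3 text under Data Analysis, state that each mediator's Week 0 (Pre-Quit) value is a covariate in both the arm-to-mediator and the mediator-to-abstinence equations. Keep the unadjusted change-score model as a sensitivity analysis, so that readers can see whether the conclusion depends on the assumption that only change matters.

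The cost is one sentence and one degree of freedom per mediator, with no new data collection. The cost in power is not always negligible: if only change matters, the mediator path loses some (about 92% to 81% at r = 0.5 under the assumed log-odds of 0.5 per SD).

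### Aim 3's proportion of treatment effect explained is written as adjusted over unadjusted effect, which is the unexplained share

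*Combined protocol and SAP*

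**What the plan says.** The Aim 3 text under Data Analysis (Statistical Analysis) fits two models for abstinence. The first has treatment without mediators; call its treatment coefficient T. The second adds the mediators, in order to "estimate the effect of treatment in the mediator adjusted model"; call that coefficient D. The plan writes both as starred betas, with a hat on the adjusted one.

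The same text says: "The path model partitions the effect of treatment on outcome into direct (and unexplained) effects vs. mediated effects". It then defines the summary statistic: "Finally, we will calculate the proportion of treatment effect explained, which is calculated as" D divided by T, in parentheses, with nothing before the ratio.

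The statistic carries the overall test: "We will then test the overall mediation hypothesis using the proportion of treatment effect explained". On the mechanics, the plan says "the standard error for this quantity is calculated using the delta method, and the mediation hypothesis will be tested using a z-test". No null value is given. Single pathways are handled separately: "Individual pathways will be tested using products of the coefficients along each path using a delta-method based z-test".

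The Aim 3 paragraph under Power names the statistic again ("The mediation hypothesis will examine the proportion of treatment effect explained") but gives no formula. For the four candidate pathways it adds: "so our type-1 error will be corrected to 0.0125". Nowhere does the document give a form with a leading 1 minus.

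**The concern.** A proportion explained should be 0 when the mediators carry none of the effect and 1 when they carry all of it. D/T runs the other way. The plan itself equates the direct part with the unexplained part, and D is that direct part.

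Two things are at stake. The first is the reported number, which would be the complement of what its label says. The second is the overall mediation conclusion. A reader or programmer would naturally test something called a proportion explained against zero. Applied to D/T, that asks whether any treatment effect remains after adjustment. A drug that works through none of the measured mediators would pass easily, and complete mediation would usually fail. With inert mediators the overall result would also contradict the plan's own pathway tests.

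The wording does not correct itself. It calls the coefficient from the model without mediators the direct effect, although that coefficient is the total effect.

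**Working it through.** **Inputs from the plan.** T and D as defined in the Aim 3 text; linear models on standardized variables; a delta-method standard error and z-test; n = 310, taken as 155 per arm; abstinence of 21.2% vs 50.3% at week 12 and 14.5% vs 33.5% at week 24 (Power, Aim 1). The plan states no value for the proportion, so there is no figure of its own to reproduce.

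**Algebra.** In linear models total = direct + mediated, so T = D + M.

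- As written: D/T = direct/total = unexplained share.
- Explained share: M/T = (T − D)/T = 1 − D/T.

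Example with the plan's week-12 rates and an assumed 20% mediated: T = 50.3 − 21.2 = 29.1 points, M = 0.20 × 29.1 = 5.82, D = 23.28. Then D/T = 0.80 and 1 − D/T = 0.20. At week 24, T = 19.0, M = 3.8, D = 15.2, again 0.80 and 0.20. Standardizing treatment rescales T and D equally, so the ratio does not change.

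**Large-sample check.** Linear models, N = 400,000, with assumed path coefficients (treatment to mediator a, mediator to outcome b, direct c):

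| Scenario (a, b, c) | T | D | D/T as written | 1 − D/T | True share ab/(c + ab) |
|---|---|---|---|---|---|
| No mediation (0, 0.3, 0.3) | 0.300 | 0.300 | 1.00 | 0.00 | 0.00 |
| Partial (0.4, 0.25, 0.2) | 0.301 | 0.201 | 0.67 | 0.33 | 0.33 |
| Full (0.5, 0.4, 0) | 0.197 | −0.002 | −0.01 | 1.01 | 1.00 |

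**The z-test.** With q = D/T, the delta method gives Var(q) ≈ [Var(D) + q²Var(T) − 2q Cov(D,T)]/T². Since 1 − q has the same variance, testing q against 1 is identical to testing 1 − q against 0. Testing q against 0 is a different test.

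**Simulation at the trial's size.** 4,000 trials per scenario, 155 per arm, binary abstinence from a latent-normal model matched to the plan's rates. Outcome models were linear, with one or four independent mediators of equal strength, and the sandwich delta-method standard error included Cov(D,T). The plan gives no treatment-to-mediator effects. The assumed values were 0, 0.5 and 1.0 SD (inert), 0.5 and 1.0 SD (20% mediated), and 1.0 and 1.25 SD (complete). The ratio was tested at two-sided 0.05. Ranges run over the number of mediators and the assumed effects.

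| Scenario | Quantity | As written (null 0) | Corrected, 1 − D/T (null 0) |
|---|---|---|---|
| Inert mediators | Rejection, week 12 | 98.9–100% | 0–4.0% |
| Inert mediators | Rejection, week 24 | 90.5–100% | 0–2.2% |
| 20% mediated | Median reported proportion | 0.80–0.81 | 0.19–0.20 |
| Complete mediation | Rejection, week 12 | 6.4–8.2% | 98.7–100% |
| Complete mediation | Rejection, week 24 | 6.2–7.0% | 76.9–98.7% |

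Under complete mediation the median D/T was 0.02–0.05. With inert mediators, a single product-of-coefficients test at 0.0125 rejected in at most 1.2% of trials.

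A simpler run with a continuous outcome (2,000 trials of 310) agrees. With no mediation the written ratio rejected against 0 in 100% of trials and the corrected form in 3.4%. With full mediation the figures were 5.7% and 99.6%.

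**The case against.** The strongest objection is that the plan never says the ratio is tested against 0. Taken literally, D/T has 1 as its no-mediation value, and an analyst could reasonably test against 1. The test would then be exactly the corrected one. This stands: the reversed conclusion depends on the null chosen. It does not rescue the reported proportion, which is wrong under either null.

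A leading 1 minus could also have been lost when the PDF was converted to text. That cannot be ruled out without the source page. But the expression reads as a complete parenthesised ratio with both terms defined in words, and nothing around it suggests a gap.

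The rejection rates rest on assumed mediator effects and on 0.05 for the overall test, since the plan does not say whether its 0.0125 applies there. That is fair, and the rates are illustrative. The inversion itself needs none of these assumptions.

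Finally, the intent is recognisable. A careful statistician would probably notice 100% explained beside four null pathways, and those pathway tests address affect and cognition directly. All true, but the written formula is what will be programmed and audited, and the plan assigns the overall hypothesis to this statistic.

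**Conclusion.** The concern holds: the formula is wrong as written. On the plan's own definitions D/T is the unexplained share, so any reported value would be 1 minus the intended one; 20% mediated would appear as about 80%. That part is algebra and holds whatever null is used, for the linear models planned. If logistic models were used, 1 − D/T would be only approximate because odds ratios are non-collapsible, but the direction of the error would be the same.

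The effect on the test is conditional. Against 0, the overall test would nearly always declare mediation when the drug works and the mediators are inert, and would seldom do so when mediation is complete. Against 1, its rejection rates are those of the corrected test.

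The pathway tests, Aim 1, Aim 2 and the sample size are not affected. This should be fixed, but it does not threaten the primary efficacy result.

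**What to change.** Check the formula against the source page. If it stands as read, make these changes under Data Analysis, Aim 3, before the analysis is run:

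- Define the proportion explained as 1 − D/T, that is, 1 minus the ratio of the mediator-adjusted to the unadjusted treatment coefficient.
- State that the z-test is of H0: proportion explained = 0. The delta-method standard error stays as it is, because adding a constant does not change it.
- Leave the product-of-coefficients pathway tests unchanged.

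The cost is one formula and one sentence. Nothing changes in data collection, sample size or the Aim 1 analysis.

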## **2. Statistical Analysis**

### **Power**

Power is provided for the primary aims since the exploratory aim is hypothesis generating. Power calculations were all approximated as t- or z-tests (2-sided,  $\alpha = .05$ ), and conducted using PASS Software (Power and Sample Size, NCSS Software, Kaysville, UT).

Aim 1: The primary analysis is a comparison in week 12 and 24 cotinine-confirmed 7-day point prevalence quit rates between placebo and varenicline. For the week 12 comparison, we based our sample size selection on the expectation that quit rates in the placebo and varenicline arms would approximate those reported in past varenicline trials with the general population of smokers (i.e., placebo = 21.2%; varenicline = 50.3%; Gonzales et al., 2006). With a sample of 310, we have >90% power to detect a significant effect between our treatment arm. Notably, we have 80% to detect a difference in week 12 quit rates if the difference between treatment arms is as small as 15%, not 29% as found in Gonzales et al. (2006), since the effect for varenicline may be smaller in this sub-group of smokers. For the week 24 comparison, we based our sample size on the expectation that the quit rate in the placebo arm would be 14.5%, vs. 33.5% for varenicline (Gonzales et al., 2006). In this case, we have 85% power to detect a significant difference between treatment arms. However, we have 80% power to detect a difference between treatment arms if the treatment arm difference is only 15%, not the 19% reported in Gonzales et al. (2006), since the effect for varenicline may be smaller in this sub-group of smokers. Even though it may appear that we are over-powered for Aim 1, we require the proposed sample to conduct the non-inferiority analyses for Aim 2.

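### Aim 3 tests each mediation pathway with a delta-method z-test that is strongly conservative at N = 310 and alpha 0.0125; the power lost depends on a mediator-to-abstinence effect the plan never states

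*Combined protocol and SAP*

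**What the plan says.** The Aim 3 text under Data Analysis fits linear models to standardized variables for both halves of each pathway: "The effects of treatment arm on mediators, and of mediators on outcome, will be assessed using linear regression and standardized variables". The decision rule for a pathway follows: "Individual pathways will be tested using products of the coefficients along each path using a delta-method based z-test". The Aim 3 paragraph under Power names the same procedure, saying the analysis "will test each mediation hypothesis with a z-score generated using the delta method".

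That paragraph also sets the multiplicity correction. It counts four pathways, two through affect and two through cognition, and concludes: "so our type-1 error will be corrected to 0.0125". It then gives the sensitivity of the design: "Our sample of 310 gives us 80% power to detect small to medium effects", with delta = 0.19, "for changes in the proposed mediators, which we have seen in previous trials". No effect size is given for the path from mediator to abstinence. The Aim 3 text plans no bootstrap, distribution-of-product or joint-significance test of the pathways. It does say that treatment will be tested as a predictor of each mediator, and each mediator as a predictor of abstinence adjusted for treatment, but it does not make that pair of tests the criterion for a pathway.

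**The concern.** A delta-method z-test treats the product of two estimated coefficients as normal. That is reasonable when at least one coefficient is many standard errors from zero. When both are only a few standard errors from zero, the product is skewed and the normal reference is too demanding, more so at a small alpha. At a standardized path of 0.19 and N = 310 each path sits about 3.3 standard errors from zero, and the corrected alpha is small.

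Aim 3 has its own hypothesis and power claim; it is not part of the exploratory aim. If the test has much less power than stated, a null mediation result would be read as evidence that affect and cognition do not carry the treatment effect, when the test had little chance of showing it. Nothing is gained in return, because tests that keep the error rate at or near its nominal level are available on the same data.

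**Working it through.** **Inputs.** From the Aim 3 power paragraph: N = 310, four pathways, alpha 0.05/4 = 0.0125, delta = 0.19, claimed power 80%. Tests are two-sided, as stated at the start of the Power section. Allocation is 1:1 (half the sample receives varenicline, Risk/Benefit Assessment). The second path, mediator to abstinence, is not in the documents; it is an assumption here and is varied from 0.10 to 0.50.

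**Step 1: the plan's figure.** The two-sided critical value at 0.0125 is 2.498. For a one-sample test, power = Φ(δ√N − 2.498). With δ√N = 0.19 × √310 = 3.345, power = Φ(0.847) = 80.2% (79.7% with a t-test). So the 80% is the power to detect one standardized effect, not a product of two.

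**Step 2: the planned statistic.** Let a and b be the two path estimates, with Za = a/SE(a) and Zb = b/SE(b). The delta-method statistic is

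Z = ab / √(b²SE(a)² + a²SE(b)²) = Za·Zb / √(Za² + Zb²).

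Suppose both paths are estimated at exactly 0.19, so Za = Zb = 3.345. Each path is significant at 0.0125, yet Z = 3.345/√2 = 2.365, below 2.498. With equal paths, each must reach 2.498 × √2 = 3.53 before the pathway is declared.

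**Step 3: error rate.** Take Za and Zb as independent normals with unit variance and means 0.19√310 and 0 (4 million draws). The z-test rejects 0.09% at a nominal 1.25%, about one-fourteenth of what is allowed. The joint-significance test, which requires both |Za| and |Zb| above 2.498, rejects 1.0%; its size cannot exceed alpha. With both paths null the figures are about 0.00006% and 0.0125² = 0.016%.

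**Step 4: power at N = 310, alpha 0.0125, first path 0.19.**

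| Second path (assumed) | Delta-method z | Joint significance | Relative loss |
|---|---|---|---|
| 0.10 | 4% | 18% | 78% |
| 0.14 | 13% | 39% | 68% |
| 0.19 | 31% | 64% | 51% |
| 0.25 | 55% | 78% | 30% |
| 0.30 | 66% | 80% | 17% |
| 0.50 | 77% | 80% | 4% |

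As the second path grows, Z tends to Za, so the ceiling for the planned test is the 80.2% of Step 1. It is still at 77% with a second path of 0.50. At the uncorrected alpha of 0.05 with both paths 0.19, the comparison is 69% against 84%.

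**Step 5: cross-checks with simulated trials.** These used a binary outcome and linear regressions.
- Mediator difference 0.38 SD between arms (a standardized path of 0.38 × 0.5 = 0.19 under 1:1 allocation) and slope 0.08 per SD: 29% for the z-test, 61% for joint significance, 64% for a Monte Carlo product interval.
- A within-arm percentile bootstrap at about the same path sizes (1,000 trials): 68.1% against 34.5% for the z-test. With the second path null, the bootstrap rejected 0.9% (first path 0.19) and 1.4% (first path 0.30), consistent with 1.25% at that number of trials.

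**Step 6: sensitivity.**
- The Accrual section allows up to 20% withdrawal. With 310 × 0.8 = 248 participants contributing and both paths 0.19, power is 17% against 48%.
- If 0.19 means a between-arm difference in SD units, the standardized first path is 0.19 × 0.5 = 0.095. With a second path of 0.19, power is 4% against 16%.
- If 0.19 were the standardized size of the product itself, the relative loss is about 2% to 6%.
- For 80% power with both paths 0.19, the z-test needs about 520 participants and the joint test about 390.

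**The case against.** The strongest reply is that the size of the loss is not a property of the plan. A reader might infer from the equal-path row that the planned test gives away half the attainable power. The documents do not support that as a general statement: 0.19 is tied to changes in the mediators, no second-path effect is given, and the loss runs from about 78% to about 4% over the range shown. If the mediators predict abstinence strongly, the z-test is nearly as good as the alternatives. This part of the reply stands, and it is why the result is given as a range. Reading 0.19 as the size of the product itself would make the loss trivial, but the wording attaches it to the mediators.

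Second, the plan already produces the two component-path tests, which are the ingredients of the joint-significance test. The evidence would therefore be available, but the plan does not use it as the rule: a pathway with both components significant can still fail the z-test, as Step 2 shows.

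Third, the error is on the safe side. A reader might infer inflated false positives, faulty confidence intervals or a defect in the proportion-explained test. None of these follows. The z-test rejects too rarely, the plan specifies no interval for the pathways, and the calculations here do not examine the proportion explained.

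**Conclusion.** The point holds for the four Aim 3 pathway tests. The conservatism at N = 310 and alpha 0.0125 follows from the plan's own sample size, alpha and 0.19: about 0.1% actual against 1.25% nominal when the other path is null. The z-test had lower power than joint significance at every second-path value examined, by an amount that cannot be fixed without an assumption the documents do not supply. The claimed 80% belongs to a one-sample test of a single effect; the planned product test does not deliver it unless the second path is well above 0.50.

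The numbers rest on treating the two path z-statistics as independent normals, which the binary-outcome simulations support at equal paths of about 0.19, and on reading 0.19 as the standardized treatment-to-mediator path. Changing the test recovers what the design can give; it does not restore 80% at equal paths of 0.19. The Aim 1 comparison of quit rates is not touched.

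**What to change.** In the Aim 3 text under both Power and Data Analysis, replace the delta-method z-test of each pathway with one pre-specified alternative:

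- a percentile bootstrap of the product of coefficients, resampling participants within arm, with a 98.75% interval; or
- a Monte Carlo product-of-coefficients interval at 98.75%; or
- the component-path tests already described, made the formal rule: a pathway is declared only if both are significant at 0.0125.

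Restate the Aim 3 power as power for the indirect effect, with the assumed mediator-to-abstinence path written down and a range around it. Say whether 0.19 is a standardized path or a between-arm difference in SD units. Make the choice before unblinded analysis of Aim 3, so that it cannot be seen as driven by results.

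The cost is small. The software named in the plan (Stata, SAS or R) suffices, and no data or visits are added. A bootstrap needs a sentence on whether the planned item imputation and data-driven covariate selection are repeated in each resample. The stated power will look less favourable than it does now.
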